7.1.3.3. Other solicited adverse events

Solicited local (**administration site**) and systemic AEs that continued beyond day 7 after vaccination will not need to be entered as an AE in the AE eCRF or the subject's source document. They will be collected via the eDiary.

Note: Any solicited adverse event that meets any of the following criteria must be entered into subjects' source document (see Section 10.2) and also as an adverse event on the Adverse Event eCRF:

- Solicited local or systemic adverse event that leads to a visit to a healthcare provider (medically attended adverse event, see Section 7.2.3.4).
- Solicited local or systemic adverse event leading to the subject withdrawing from the study or the subject being withdrawn from the study by the investigator (adverse event leading to withdrawal).

Solicited local or systemic adverse event that otherwise meets the definition of a serious adverse event (see Section 7.1.2).

7.1.4. Unsolicited Adverse Events

An unsolicited adverse event is an adverse event that was not solicited using a Subject Diary and that was spontaneously communicated by a parent(s)/LAR(s) who has signed the informed consent.

Unsolicited AEs will be collected during interview with the parent(s)/LAR(s) and by review of available medical records at the next visit. Unsolicited AEs will be reviewed at the safety follow-up calls as well.

Parent(s)/LAR(s) will be instructed to contact the site as soon as possible to report potential unsolicited AEs that required hospitalization, or emergency room visit, or visit to/by a health care provider that were of concern to the parent(s)/LAR(s). The detailed information about the reported unsolicited AEs will be collected by the qualified site personnel during the interview and will be documented in the subject's records.

All subjects' parent(s)/ legal guardian(s) will be instructed to contact the site in case their child experiences unsolicited AEs which persist beyond 30 days after study vaccination.

7.1.5. Clinical laboratory parameters and other abnormal assessments qualifying as adverse events or serious adverse events

In absence of diagnosis, abnormal laboratory findings (e.g. clinical chemistry, hematology, urinalysis) or other abnormal assessments (e.g. x-ray imaging studies) that are judged by the investigator to be clinically significant will be recorded as AE or SAE if they meet the definition of an AE or SAE (refer to Sections 7.1.1 and 7.1.2). Clinically significant abnormal laboratory findings or other abnormal assessments that are present at baseline and significantly worsen following the start of the study will also be reported as AEs or SAEs. The investigator will exercise his or her medical and scientific judgement in deciding whether an abnormal laboratory finding or other abnormal assessment is clinically significant.

7.1.6. Adverse events of special interest

Adverse events of special interest (AESIs) are predefined (serious or non-serious) AEs of scientific and medical concern specific to the product or program, for which ongoing monitoring and rapid communication by the investigator to the sponsor can be appropriate, because such an event might warrant further investigation in order to characterize and understand it.

7.1.6.1. Febrile seizures

Seizures are defined according to the Brighton Collaboration Working Group (BCWG) case definition of generalized convulsive seizure as an adverse event following immunization [[Bonhoeffer](#), 2004].

The list of Preferred Terms (PTs) corresponding to the diagnosis of seizure, are those included in the Medical Dictionary for Regulatory Activities (MedDRA) Standard MedDRA Query (SMQ) Narrow “Generalized convulsive seizures following immunization”.

For any new diagnosis of generalized convulsive seizure (including febrile seizure), irrespective of seriousness, the investigator (or designate) must complete, an electronic Expedited Adverse Events Report and an ad-hoc eCRF page on seizures to further characterize this AESI.

7.1.6.2. Arthritis

Cases of arthritis are defined according to the following ad-hoc definition:

- Presence of a physical exam findings of swelling, redness, heat, or limitation in range of motion and/or
- Presence of a diagnostic imaging studies interpreted by a health care provider as demonstrating evidence of joint inflammation and/or arthrocentesis results evidencing inflammation.

Due to the heterogeneity of the presentation of arthritis which can be either acute or chronic, the threshold of duration of symptoms of 6 weeks is to be considered.

The list of PTs corresponding to the diagnosis of arthritis, are those included in the MedDRA SMQ Narrow “Arthritis”. For any new diagnosis of arthritis (serious or non-serious) in a study subject, the investigator (or designate) must complete, an electronic Expedited Adverse Events Report and an ad-hoc eCRF page on arthritis to further characterize this AESI.

7.1.6.3. Potential immune-mediated diseases

Potential immune-mediated diseases (pIMDs) are a subset of AEs that include autoimmune diseases and other inflammatory and/or neurologic disorders of interest which may or may not have an autoimmune aetiology. The AEs that need to be recorded and reported as pIMDs include those listed in [Table 12](#).

However, the investigator will exercise his/her medical and scientific judgement in deciding whether other diseases have an autoimmune origin (i.e. pathophysiology involving systemic or organ-specific pathogenic autoantibodies) and should also be recorded as a pIMD.

Table 12 List of Potential Immune-Mediated Diseases

Neuroinflammatory disorders	Musculoskeletal disorders	Skin disorders

 • Cranial nerve neuropathy, including paralysis and paresis (e.g. Bell's palsy). • Optic neuritis. • Multiple sclerosis. • Transverse myelitis. • Guillain-Barré syndrome, including Miller Fisher syndrome and other variants. 	
 • Systemic lupus erythematosus and associated conditions • Systemic scleroderma (Systemic sclerosis), including: 
 - Diffuse Scleroderma - CREST syndrome • Idiopathic inflammatory myopathies, including: 
 - Dermatomyositis - Polymyositis 	
 • Psoriasis. • Vitiligo. • Erythema nodosum. • Autoimmune bullous skin diseases (including pemphigus, pemphigoid and dermatitis herpetiformis). • Lichen planus. • Sweet's syndrome.


 • Acute disseminated encephalomyelitis, including site specific variants e.g.: non-infectious encephalitis, encephalomyelitis, myelitis, myeloradiculoneuritis. • Myasthenia gravis, including Lambert-Eaton myasthenic syndrome. • Demyelinating peripheral neuropathies including: 
 - Chronic inflammatory demyelinating polyneuropathy, - Multifocal motor neuropathy - Polyneuropathies associated with monoclonal gammopathy. • Narcolepsy. 	
 • Anti-synthetase syndrome. • Rheumatoid Arthritis and associated conditions including: 
 - Juvenile Idiopathic Arthritis - Still's disease. • Polymyalgia rheumatica. • Spondyloarthropathies, including: 
 - Ankylosing Spondylitis, - Reactive Arthritis (Reiter's Syndrome), - Undifferentiated Spondyloarthritis, - Psoriatic Arthritis, - Enteropathic arthritis. • Relapsing Polychondritis. • Mixed Connective Tissue disorder. • Gout. 	
 • Localized Scleroderma (Morphea).
Vasculitis	Blood disorders	Others

 • Large vessels vasculitis including: 
 - Giant Cell Arteritis (Temporal Arteritis), - Takayasu's Arteritis. • Medium sized and/or small vessels vasculitis including: 
 - Polyarteritis nodosa, - Kawasaki's disease, - Microscopic Polyangiitis, - Wegener's Granulomatosis (granulomatosis with polyangiitis), 	
 • Autoimmune hemolytic anemia. • Autoimmune thrombocytopenia. • Antiphospholipid syndrome. • Pernicious anemia. • Autoimmune aplastic anemia. • Autoimmune neutropenia. • Autoimmune pancytopenia. 	
 • Autoimmune glomerulonephritis including: 
 - IgA nephropathy, - Glomerulonephritis rapidly progressive, - Membranous glomerulonephritis, - Membranoproliferative glomerulonephritis, - Mesangioproliferative glomerulonephritis. - Tubulointerstitial nephritis and uveitis syndrome.

 - Churg-Strauss syndrome (allergic granulomatous angiitis or eosinophilic granulomatosis with polyangiitis), - Buerger's disease (thromboangiitis obliterans), - Necrotizing vasculitis 		
 • Ocular autoimmune diseases including: 
 - Autoimmune uveitis - Autoimmune retinitis. • Autoimmune myocarditis. • Sarcoidosis. • Stevens-Johnson syndrome. • Sjögren's syndrome.

 - (cutaneous or systemic), - anti-neutrophil cytoplasmic antibody (ANCA) positive vasculitis (type unspecified), - Henoch-Schonlein purpura (IgA vasculitis), - Behcet's syndrome, - Leukocytoclastic vasculitis. 		
 • Alopecia areata. • Idiopathic pulmonary fibrosis. • Goodpasture syndrome. • Raynaud's phenomenon.
Liver disorders	Gastrointestinal disorders	Endocrine disorders

 • Autoimmune hepatitis. • Primary biliary cirrhosis. • Primary sclerosing cholangitis. • Autoimmune cholangitis. 	
 • Inflammatory Bowel disease, including: 
 - Crohn's disease, - Ulcerative colitis, - Microscopic colitis, - Ulcerative proctitis. • Celiac disease. • Autoimmune pancreatitis. 	
 • Autoimmune thyroiditis (Hashimoto thyroiditis). • Grave's or Basedow's disease. • Diabetes mellitus type I. • Addison's disease. • Polyglandular autoimmune syndrome. • Autoimmune hypophysitis.

When there is enough evidence to make any of the above diagnoses, the AE must be reported as a pIMD. Symptoms, signs or conditions which might (or might not) represent the above diagnoses, should be recorded and reported as AEs but not as pIMDs until the final or definitive diagnosis has been determined, and alternative diagnoses have been eliminated or shown to be less likely.

In order to facilitate the documentation of pIMDs in the eCRF, a pIMD standard questionnaire and a list of MedDRA preferred terms (PTs) and PT codes corresponding to the above diagnoses will be available to investigators at study start.

7.2. Detecting and recording adverse events and serious adverse events

7.2.1. Time period for detecting and recording adverse events and serious adverse events

All AEs starting within 30 days following administration of each dose of study vaccines (Day 1 to Day 30 postvaccination) must be recorded onto/into the appropriate section of the eCRF, irrespective of intensity or whether or not they are considered vaccination-related.

The time period for collecting and recording SAEs will begin at Day 1 (ie, the first receipt of study vaccines) and will end 6 months or 12 months following administration of the last dose of study vaccine for each subject (ie, study end). See Section 7.3 for instructions on reporting of SAEs.

All medically attended AEs will be collected and recorded from Day 1 (ie, the time of the first receipt of study vaccines) until 6 months or 12 months following administration of the last dose of study vaccine for each subject (ie, study end).

All AEs/SAEs leading to withdrawal from the study will be collected and recorded from Day 1 (ie, the time of the first receipt of study vaccines) until 6 months or 12 months following administration of the last dose of study vaccine for each subject (ie, study end).

In addition to the above-mentioned reporting requirements and in order to fulfil international reporting obligations, SAEs that are related to study participation (i.e. protocol-mandated procedures, invasive tests, a change from existing therapy) or are related to a concurrent GSK medication/vaccine will be collected and recorded from the time the subject consents to participate in the study until she/he is discharged from the study.

The time period for collecting and recording of AESIs will begin at Day 1 (ie, the first receipt of study vaccines) and will end 6 months or 12 months following administration of the last dose of study vaccines (ie, study end). See section [7.3](#) for instructions on reporting of AESIs. Details regarding follow-up of AEs, SAEs and AESIs are given in Section [7.4](#).

An overview of the protocol-required reporting periods for AEs, SAEs, medically attended AEs and AESIs is given in [Table 13](#).

Table 13 Reporting Periods for Collecting Safety Information

Event	Pre-V1 ¹	V1	D16	D31	V2	D76	D91	V3	D136	V4	D181	D241	V5	D 316	V6	D361,	V7
			D1		D61 (2 M post- vacc 1)			D121 (2 M post- vacc 2)		D151 (1 M post- vacc 3)		D301 (6 M post- vacc 3)		D331 (1 M post- vacc 4)		421, 481, 541, 601 ²	D481 or D661 (6 M or 12 M post- vacc 4) ³
Solicited local and systemic AEs ⁴																	
All Unsolicited AEs																	
AEs/SAEs leading to withdrawal from the study																	
SAEs (including SAEs related to study vaccine(s))																	
SAEs related to study participation or concurrent GSK medication/vaccine																	
AESIs																	
Medically attended AEs																	
COVID-19 infection related AEs																	

M: month, V: Visit; D: Day, AE: adverse event, SAE: serious adverse event, AESI: adverse event of special interest, COVID-19: Coronavirus Disease 2019.

CONFIDENTIAL

205239 (MENB REC 2ND GEN-023 [V72_57])
Protocol Amendment 8 Final

Note: All concomitant medications/products, except vitamins and dietary supplements, administered during the 30-days postvaccination period as well as those used to treat an AE or a SAE (throughout the study period), should be recorded in the eCRF and subject medical records.

¹ After informed consent is obtained.

²For subjects who have not yet reached the 6-month safety follow-up after the last dose at the time protocol amendment 7 takes effect, follow-up calls on Day 481, Day 541 and Day 601 will not be performed.

³For subjects who have not yet reached the 6-month safety follow-up after the last dose at the time protocol amendment 7 takes effect, Visit 7 will occur on Day 481.

⁴Solicited AEs to be collected for 7 days following each vaccination, with ongoing solicited AEs collected until resolution or day 30, whichever occurs first. Specific solicited systemic AEs (parotid gland swelling, fever, rash) will be collected for 30 days following MMR/V vaccination a Visit 5 (Day 301).

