2. OBJECTIVES AND ENDPOINTS

Objectives	Endpoints

 To assess the safety and tolerability of rMenB+OMV NZ, PCV13 and other RIV when administered concomitantly to healthy infants at 2, 4, 6 and 12 months of age, throughout the study duration. 	
 The percentages of subjects with solicited local Adverse events (AEs) (administration site event) and systemic AEs during the 7 days (including the day of vaccination) after the 1st, the 2nd, the 3rd and the 4th vaccination (Visits 1, 2, 3 and 5). The percentages of subjects with solicited systemic AEs of parotid/salivary gland swelling, fever and rash during the 30 days (including the day of vaccination) after the 4th vaccination (Visit 5). The percentages of subjects with all unsolicited AEs (including SAEs, AEs leading to withdrawal, AESIs, and medically attended AEs) during 30 days (including the day of vaccination) after the 1st, the 2nd, the 3rd and the 4th vaccination (Visits 1, 2, 3 and 5). The percentages of subjects with SAEs, AEs leading to withdrawal, AESIs and medically attended AEs from study Day 1 (Visit 1) until study end (6 months or 12 months after last study vaccination, Visit 7*).

 To demonstrate the sufficiency of the immune response to rMenB+OMV NZ when administered concomitantly with PCV13 and other RIV to healthy infants at 2, 4 and 6 months of age, at one month after the 3rd vaccination. 
Criteria: The sufficiency of the immune response to rMenB+OMV NZ at one month after the 3rd vaccination will be demonstrated if the adjusted lower confidence limit for the percentage of subjects achieving serum bactericidal assay using human complement (hSBA) titers \geq Lower Limit of Quantitation (LLOQ) is \geq 60% for the N. meningitidis serogroup B test strains M14459, 96217, NZ98/254, M13520 (individually); and is \geq 50% for all strains combined (composite endpoint).
	
 At 1 month after the 3rd vaccination (Day 151): 
 the percentages of subjects with hSBA titers \geqLLOQ; for each of the M14459, 96217, NZ98/254 and M13520 test strains. the percentages of subjects with hSBA titers \geqLLOQ for all strains combined (composite endpoint).

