5.6.16.2. Safety follow-up calls

During the course of the trial, a total of 10 or 13 safety follow-up calls will be performed. Safety follow-up calls will be performed on the following time points:

Treatment period:

- Day 16 and Day 31 (15 and 30 days post 1st vaccination, respectively),
- Day 76 and Day 91 (15 and 30 days post 2nd vaccination, respectively),
- Day 136, Day 181 and Day 241 (15, 60 and 120 days post 3rd vaccination, respectively),
- Day 316 (15 days post 4th vaccination).

Follow-up period:

- Day 361, Day 421, Day 481, Day 541 and Day 601 (60, 120, 180, 240, and 300 days post 4th vaccination, respectively). For subjects who have not yet reached the 6-month safety follow-up after the last dose at the time protocol amendment 7 takes effect, Visit 7 will occur on Day 481 instead of the follow-up call, and follow-up calls at Day 541 and Day 601 will not be performed.

Safety follow-up calls are calls made to the subject's parent(s)/LAR(s) by a qualified healthcare professional designated on the site log. These calls will follow a script which will facilitate the collection of relevant safety information. The subject's parent(s)/LAR(s) will be interviewed according to the script, and information relating to unsolicited AEs [including serious adverse events (SAEs), AESIs, medically attended AEs, and AEs leading to vaccine/study withdrawal] and concomitant medications or vaccinations associated with those events. All safety information described by the subject's parent(s)/LAR(s) must be written down in a designated location within the source document and not written on the script used for the telephone call.

The site should schedule the next study activity (clinic visit or safety call) with the subject's parent(s)/LAR(s).

The subject's parent(s)/LAR(s) will be reminded to contact the site if there are any questions and to contact the site immediately (or as soon as the subject is medically stable) if the subject has a medical condition that leads to a hospitalization or an emergency room visit.

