6.5. Contraindications to subsequent vaccination

The following events constitute absolute contraindications to further administration of **vaccines specified in the protocol**. If any of these events occur during the study, the subject must not receive additional doses of vaccines but may continue other study procedures at the discretion of the investigator (see Section 7.4).

- Anaphylaxis following the administration of vaccines.
- Occurrence of a new pIMD or the exacerbation of an existing pIMD. Refer to Section 7.1.6.2 for the definition of pIMDs.
- Any occurrence of an event listed in the exclusion criteria which must be always re-assessed by the investigator before administration of the next dose of study vaccine. Refer to Section 4.2.
- Subjects who experience any SAE judged to be possibly or probably related to study vaccine, including hypersensitivity reactions.

- Subjects who develop any new condition which, in the opinion of the investigator, may pose additional risk to the subject if he/she continues to participate in the study.

The following events constitute contraindications to administration of rMenB+OMV NZ at that point in time; if any of these events occur at the time scheduled for vaccination, the subject may be vaccinated at a later date, within the time window specified in the protocol (see Section 5.5).

- Body temperature elevation [$\geq 100.4^{\circ}$ F ($\geq 38.0^{\circ}$ C)] within the previous 3 days.
- Significant acute illness within the previous 7 days.
- Use of antipyretics and/or analgesic medications within the previous 6 hours.
- Receipt of, or plan to receive, any other vaccine(s) than those listed as study or non-study vaccines, within 14 days (or 28 days for live attenuated vaccines and 7 days for influenza vaccines) of study vaccination.

For contraindications to administered other study vaccines, refer to their approved product label/package insert.

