8.2.2. Subject withdrawal from study vaccine(s)

A ‘withdrawal’ from the study vaccine(s) refers to any subject who does not receive the complete treatment, i.e. when no further planned dose is administered from the date of withdrawal. A subject withdrawn from the study vaccine(s) may not necessarily be withdrawn from the study as further study procedures or follow-up may be performed (safety or immunogenicity) if planned in the study protocol.

Information relative to premature discontinuation of the study vaccine(s) will be documented on the Vaccine Administration page/screen of the eCRF. The investigator will document whether the decision to discontinue further vaccination/treatment was made by the subject’s parent(s)/LAR(s), or by the investigator, as well as which of the following possible reasons was responsible for withdrawal:

- Serious adverse event.
- Unsolicited non-serious adverse event.
- Solicited adverse event
- Not willing to be vaccinated
- Other (specify).

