### **5.1.2. Additional considerations**

The number of subjects with suspected, probable or confirmed COVID-19 infection will be summarized by vaccine group and across diagnoses. This summary will be provided for the Exposed Set.

The number of exposed participants who discontinued the study will be tabulated by vaccine group with the reason for discontinuation. The summary table will be produced by relationship to COVID-19.

A summary table of important protocol deviations by relationship (related/not related) to COVID-19 will be provided.

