#### *Analysis of Unsolicited Adverse Events*

This analysis applies to all AEs occurring during the study, judged either as reasonable possibly related, or not reasonable possibly related to vaccination by the investigator, recorded in AE eCRF, with a start date on or after the date of first vaccination. All AEs starting prior to the first vaccination will only be listed. The original verbatim terms used by investigators to identify AEs in the eCRFs will be mapped to preferred terms using the MedDRA dictionary. The AEs will then be grouped by MedDRA preferred terms into frequency tables (with 95% CI; [Frank, 2009; Clopper, 1934]) according to system organ class.

All reported AEs, as well as AEs judged by the investigator as related to study vaccine, will be summarized according to system organ class and preferred term within system organ class. These summaries will be presented by vaccine group and by interval of study observation. When an AE occurs more than once for a subject, the maximal severity and strongest relationship to the vaccine group will be counted.

Serious adverse events, withdrawal due to AEs and AESIs will be described in detail.

Separate summaries will be produced for the following categories:

- Serious adverse events (SAE)
- Adverse events related to vaccine
- Adverse events of special interest (pIMDs, seizures, and/or arthritis)
- Adverse event leading to withdrawal with relationship to COVID-19
- Adverse events leading to a medically attended visit

These summaries will also be presented by the 0-6/0-12 months safety follow-up periods after the last study vaccination.

Data listings of all AEs will be provided by subject. In addition, AEs in the categories above will be provided as listed data.

Descriptive summary statistics will be provided for subgroups gender, race, ethnic origin and age group (6-8 weeks or  $\geq 8$  weeks), for the following parameters:

- Adverse events
- Adverse events related to vaccine
- Serious adverse events (SAE)
- Adverse events leading to a medically attended visit

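### The safety endpoint on AEs leading to withdrawal does not say whether it means leaving the study or stopping vaccine, and no specified summary shows AE-driven vaccine stops by group

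*Protocol*

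**What the plan says.** The endpoint in protocol section 2, repeated in SAP section 3, is "The percentages of subjects with SAEs, AEs leading to withdrawal, AESIs and medically attended AEs from study Day 1 (Visit 1) until study end". It does not say what the infant withdraws from.

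Protocol 8.2 keeps two statuses apart. Withdrawal from the study (8.2.1) means not returning for the concluding visit. Withdrawal from study vaccine (8.2.2) means receiving no further planned dose, and the infant may remain in the study. Section 6.5 sets up that second status for infants who meet an absolute contraindication: "the subject must not receive additional doses of vaccines but may continue other study procedures at the discretion of the investigator".

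The collection rules do not agree on which status matters. Section 7.2.1 says "All AEs/SAEs leading to withdrawal from the study will be collected and recorded from Day 1". Section 7.1.3.3 sends a solicited reaction to the AE eCRF on this ground only if it is a "Solicited local or systemic adverse event leading to the subject withdrawing from the study", or if the investigator withdraws the infant from the study. The follow-up call script in 5.6.16.2 asks for "AEs leading to vaccine/study withdrawal", and the early termination procedures in 5.6.17 use the same wider scope.

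Vaccine stops are recorded: "Information relative to premature discontinuation of the study vaccine(s) will be documented on the Vaccine Administration page/screen of the eCRF". The listed reasons in 8.2.2 include a serious AE, an unsolicited non-serious AE and a solicited AE.

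On the output side, SAP 5.1.2 says "The number of exposed participants who discontinued the study will be tabulated by vaccine group with the reason for discontinuation". SAP 5.2.1 tabulates vaccinations received by group and vaccination number. SAP 5.4.1.1 lists the category "Adverse event leading to withdrawal with relationship to COVID-19".

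**The concern.** The primary safety objective is the safety and tolerability of a four-dose schedule, and the background section of the protocol describes frequent reactogenicity and raised fever rates in infants. Not completing the series because of a reaction is a direct measure of tolerability. If the withdrawal component counts only infants who leave the study, it measures retention as much as tolerability: the better a site is at keeping a stopped infant in follow-up, the lower the reported figure. A difference between MenB+PCV and Placebo+PCV in AE-driven stopping would then have no planned summary, even though SAP 5.4.1.2 provides for between-group confidence intervals on safety outcomes.

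**Working it through.** The documents state no rate of AE-related withdrawal or vaccine discontinuation, so there is no figure to reproduce. The check is to follow the word *withdrawal* from endpoint to output.

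**Step 1: what each section ties it to.**

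| Place | Scope |
|---|---|
| Protocol 2 and SAP 3 (endpoint) | not stated |
| Protocol 5.6.1 | study |
| Protocol 7.1.3.3 (solicited AE to AE eCRF) | study |
| Protocol 7.2.1 | study |
| Protocol Table 13 (row label) | study |
| Protocol 8.2.1 (flag on the AE page) | study |
| Protocol 5.6.16.2 (calls) | vaccine or study |
| Protocol 5.6.17 (early termination) | vaccine or study |

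No sentence says which scope governs the endpoint. Section 5.6.17 adds a further tension. It applies the early termination procedures to withdrawal from treatment as well as from the study, and closes with the termination page as the end of participation. Sections 6.5 and 8.2.2 let the same infant continue.

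**Step 2: follow four infants who stop vaccine and return for Visit 7.** Under 8.1 each has completed the study, so under the study-only rule none counts as an AE leading to withdrawal.

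- *Stopped for a related SAE.* Counted in the same endpoint through its SAE component, and summarised and described as an SAE.
- *Stopped for a new, non-serious immune-mediated disease.* Counted in the same endpoint through its AESI component.
- *Stopped for a non-serious solicited reaction that was not medically attended.* The reaction appears in the solicited tables by severity and group. Section 7.1.3.3 does not send it to the AE eCRF. The Vaccine Administration page is the only specified place that records it as the reason for stopping.
- *Stopped for a non-serious AE that is not an AESI and not medically attended, starting more than 30 days after a dose.* Section 7.2.1 has no collection rule for it, although the calls in 5.6.16.2 would pick it up. The window exists: Table 6 gives optimal intervals of 60, 60 and 180 days between successive vaccination visits.

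**Step 3: look for a planned output that links the stop to the AE.** SAP 5.1.2 gives reasons, but for leaving the study. SAP 5.2.1 shows how many infants received each vaccination, without reasons for missed doses. SAP 5.4.1.1 summarises AEs by type and lists every AE by subject, but has no category for discontinuing vaccine. No summary in the SAP text uses the reason recorded under 8.2.2.

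**The case against.** The case on the other side is substantial and narrows the point.

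A reader might infer that these tolerability stops are reported nowhere. The documents do not support that. The AE behind the stop appears in the solicited, unsolicited, SAE, AESI or medically attended summaries as applicable; AEs are listed by subject; missed doses show in the exposure table; and the reason is on the eCRF. What is missing is the summary that joins the stop to its cause.

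Some of the absolute contraindications in 6.5 are themselves SAEs or AESIs, so those infants already count in the same endpoint sentence. A medically attended reaction does too. The group left uncounted is smaller than the full list in 6.5 suggests.

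The endpoint wording could be read broadly, and 5.6.16.2 and 5.6.17 lean that way. Exclusion therefore follows from the study-only rule, not from the endpoint text. This stands, and it is why the defect is first one of definition.

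A reader might also take the SAP phrase about COVID-19 as limiting the withdrawal summary to COVID-related events. SAP 5.1.2 uses the same kind of wording for a related/not-related breakdown of discontinuations and protocol deviations. A breakdown is the natural reading here as well, so no error is claimed on that wording.

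Finally, the full table list is in the output and programming specification (SAP section 9), which is not among the documents. A suitable table may exist there. It would not settle the endpoint definition or the conflict between sections.

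**Conclusion.** The point holds in this form: the endpoint term is undefined, the collection rules conflict, and under the study-only rule an infant stopped from vaccination for an AE but followed to Visit 7 is not counted as an AE leading to withdrawal. No summary specified in the protocol or SAP text shows AE-driven vaccine discontinuation by group.

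The direction is known: a count limited to study withdrawal can be no higher than one that also includes vaccine discontinuation. The size is not known. The documents give no rate from which to say how many of the planned 800 and 400 infants would be affected, and any count would be invented. The clearest loss is stops for non-serious reactions that are neither AESIs nor medically attended, including solicited ones.

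The conclusion rests on the study-only sections governing the endpoint and on the SAP text alone. It is worth correcting because it affects how a primary tolerability result is reported, but it does not touch the immunogenicity conclusions or suggest that the AEs themselves go uncollected in general.

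**What to change.** 1. In protocol section 2 and SAP section 3, define the component as AEs, solicited or unsolicited, leading to withdrawal from the study or to discontinuation of study vaccination, and report the two parts separately.
2. Align protocol 5.6.1, 7.1.3.3, 7.2.1, Table 13 and the AE-page flag in 8.2.1 with the wider scope already used in 5.6.16.2 and 5.6.17. Reconcile the termination-page step in 5.6.17 with 8.2.2.
3. Add to SAP 5.4.1.1 a descriptive table of AE-related vaccine discontinuation by group and by dose, using the reason categories on the Vaccine Administration page: serious AE, unsolicited non-serious AE, solicited AE.

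If a protocol amendment is no longer practical, state the definition in the SAP and record it in SAP section 8 as a change from the planned analyses.

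The cost is one table and some wording. The reason field exists, so no new data collection is needed for a table by reason category. Section 8.2.2 does not say that the specific AE is identified on that page, so a breakdown by preferred term may not be possible and should not be promised. The reported rate may look less favourable. No rule on when vaccination stops is changed.
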